# Summary

In this investigator-initiated randomised, double-blinded clinical trial, we aim to investigate the safety and pilot-efficacy of faecal microbiota transplantation (FMT) as an adjuvant to the treatment of severe gastrointestinal neuropathy in patients with diabetes mellitus type 1 (DM1). The study results will provide the information necessary to design a sufficiently powered clinical trial with FMT in this debilitating condition.

DM1 is often complicated by gastrointestinal symptoms such as diarrhea, nausea, vomiting, abdominal pain, constipation, and faecal incontinence. These may be caused by intestinal neuropathy which predisposes to abnormal amount and composition of microbiota in the gut. FMT from a healthy donor to a patient could potentially change the microbiota in the gut and reduce gastrointestinal symptoms in DM1. FMT aims to restore a disrupted gut microbiota and amend imbalances through establishment of a stable, complex microbiota.

The clinical trial will be conducted in accordance with this protocol, the principles for Good Clinical Practice (GCP), and the Declaration of Helsinki. It will be initiated following approval from the Central Denmark Region Ethical Committees and the Danish Patient Safety Authority. If the protocol is approved and permission to start patient inclusion is issued by the GCP Unit, patient inclusion may begin after 01 January 2021 and last until 31 December 2023.

# Abbreviations

٨E	A decome account
AE	Adverse event
AUH	Aarhus University Hospital
BS	Bristol stool chart
CDI	Clostridioides difficile infection
CEFTA	Center for Faecal Microbiota Transplantation
CTT	Colorectal transit time
DM1	Diabetes mellitus type 1
eCRF	Electronic case report form
EPJ	Electronic patient journal
FMT	Faecal microbiota transplantation
GI	Gastrointestinal
GCP	Good clinical practice
GET	Gastric emptying
GSRS-IBS	Gastrointestinal syndrome rating scale - irritable bowel syndrome version
IBS-IS	The irritable vowel syndrome impact scale
ICF	Informed consent form
PAGI-SYM	Patient assessment of upper gastrointestinal symptom severity index
SADE	Serious Adverse Device Effect
SAE	Serious adverse event
SBTT	Small bowel transit time
SOP	Standard operating procedure
TGA	Transglutaminase antibody
TMF	Trial master file
WMC	Wireless motility capsule

# 1.0 Original title

Faecal microbiota transplantation for patients with diabetes mellitus type 1 and severe gastrointestinal neuropathy: a randomised, double-blinded safety and pilot-efficacy study.

# 2.0 Purpose of the study

# 2.1 Aim

The aim of the study is to evaluate the feasibility, safety and pilot-efficacy of faecal microbiota transplantation (FMT) as a treatment of severe gastrointestinal neuropathy in patients with diabetes mellitus type 1 (DM1).

# 2.2 Problem statement

DM1 may cause damage to nerve cells in the gut causing neuropathy that leads to changes in gastric and intestinal motility. This change predisposes to an abnormal amounts and composition of bacteria in the gut, probably leading to uncontrollable diarrhea and severely impaired quality of life. Transferal of intestinal microbiota from a healthy donor to a patient is called FMT. FMT may potentially change the bacteria in the gut and reduce gastrointestinal symptoms. However, FMT may also have potential side effects, especially in persons with autonomic neuropathy and delayed transit through the gut.

# 2.3 Hypotheses

## 2.3.1 Primary H0

1. Oral intake of FMT capsules is safe and well tolerated in patients with DM1, including those with prolonged gastric emptying and small intestinal transit.

## 2.3.2 Secondary H0

2. Oral intake of FMT changes the microbiota of the colon and the effect lasts for at least 4 weeks.

3. Oral intake of FMT is superior to placebo in reducing gastrointestinal symptoms in patients with DM1.

4. The effect of two doses of oral intake of FMT (separated by 4 weeks) is superior to one dose.

# 2.4 Endpoints

## 2.4.1 Primary endpoint

Number of adverse events of severity grade 2 or more assessed by CTCAE v5.0 during the first week after first intervention (FMT or placebo).

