## 2.4.2 Secondary endpoints

Patient-reported outcomes are obtained from the bowel habit diary. Each patient fills out the diary every day for one week at baseline, for one week starting at each day of the two interventions

and for one week at the follow-up at week 26. Bivariate comparions are made, comparing differences between FMT and placebo at a) Baseline vs first intervention, b) Baseline vs second intervention, c) Baseline vs longterm follow-up (week 26) for the following variables:

- 1. Median stool consistency (Bristol scale)
- 2. Number of passages of hard stools (BS 1-2)
- 3. Number of passages of liquid stools (BS 6-7)
- 4. Median number of bowel openings per 24 hours
- 5. Number of nightly bowel openings (from bedtime until morning)
- 6. Number of episodes with involuntary defaecation
- 7. Glycemic control measured by patient reported use of insulin (IE)

Patient-reported measures from the schedule of side effects and telephone call 1 week after each intervention

- 8. Mild adverse events (grade 1) following FMT or placebo assessed by CTCAE v5.0
- 9. Adverse events in week 5-8
- 10. Serious adverse events during longterm follow-up

Patient-reported outcomes from questionnaires completed at baseline and 4 weeks after each intervention period and at 26 weeks follow-up. Bivariate comparisons baseline vs week 4, baseline vs week 8, baseline vs week 26:

- 11. Change in Gastrointestinal syndrome rating scale irritable bowel version questionnaire (GSRS-IBS)
- 12. Change in patient assessment of upper gastrointestinal symptom severity index (PAGI-SYM)
- 13. Change in irritable bowel syndrome impact scale (IBS-IS)

Objective measures from the wireless motility capsule performed at baseline and 4 weeks after each intervention period:

- 14. Transit time through the small intestine
- 15. Colonic transit time
- 16. pH drop from the small intestine to the colon

Objective measures from the low-dose CT scan performed at baseline and 4 weeks after the first intervention period:

- 17. Volume of the a) small intestine and b) the colon
- 18. Volume of gas in a) the small intestine and b) the colon

Objective measures from the breath test performed at baseline and 4 weeks after the first intervention period:

19. Rise in hydrogen PPM measured in breath test for small intestinal bacterial overgrowth

Microbiota analysis on faecal samples collected at baseline and 4 weeks after each intervention period:

20. Alpha-diversity of faecal microbiota, 16S

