# 3.0 Methods and their justification

## 3.1 Study design

The study is a 8-week, randomised, double-blinded, placebo-controlled pilot trial of oral FMT versus placebo in patients with DM1 and severe GI neuropathy. The intervention period consists of a first 4 weeks where patients receive either FMT or placebo and a second 4 weeks where all patients receive FMT (Figure 1 and 2). The patients will undergo the investigations before and after each 4-week period. When the patients have completed the study period, they will be contacted by telephone every second month for two years. They will be asked about their gastrointestinal symptoms. The patients will be offered further treatment with FMT, if they experience relapse of symptoms and a score of or above 40 in the GSRS-IBS questionnaire.

The design is chosen to allow the evaluation of the safety and tolerability of FMT in patients with DM1. We will also be able to evaluate if FMT is superior to placebo, how it affects the intestinal microbiota and if the effects of two doses of oral FMT is superior to one dose.

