## 6.1.1.1 Reporting adverse events

Sponsor-investigator is responsible for the monitoring of possible unexpected side effects and AE occurring to patients in the investigation. All unexpected severe side effects (SUSARs) will

be reported to the Danish Patient Safety Authority who is the overall regulating authority for the research project, and to Ethics Committee. The Danish Patient Safety Authority will be notified by the electronic report form "reporting suspicion of serious adverse events during removal, testing, etc. of tissues/cells" (https://stps.dk/da/tilsyn/blod,-vaevceller-og-organer/vaev-og-celler/bi-virkninger-og-uoenskede-haendelser/mistanke-haendelse/). If the SAE is categorized as a "Utilsigtet hændelse", it is reported to the Danish patient safety database

(https://stps.dk/da/laering/utilsigtede-haendelser/), and a core cause analysis is carried out according to local standards at AUH. Once the core cause analysis is completed, the Danish Patient Safety Authority will receive the electronic report form "report conclusion of investigation of serious adverse events during removal, testing, etc. of tissues/cells" (https://stps.dk/da/tilsyn/blod,vaevceller-og-organer/vaev-og-celler/bivirkninger-og-uoenskede-haendelser/konklusion-haendelse/).

All AE, AR, SAE and SUSAR are documented in patient-specific case report form (CRF) at the clinical attendances or by the telephone call that is made to each patient 1 week after each intervention. SUSARs occurring during the trial are reported as soon as possible and within 24 hours of notification. The project manager and sponsor-investigator are informed of all UAR, SAE and SUSAR and regularly review trial patients' CRF and are responsible for reporting.

Annually, safety reports are generated with an overview of all expected an unexpected serious incidents and side effects during the period, which are reported to the Danish Patient Safety Authority and the Ethics Committee. The annual safety report will contain information about potential AE in the trial period, evaluation of the severity and risks-benefit according to the AE. At the end of the project, an overall final report is made.

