The connection to the study ends when a participant has completed the second intervention period, after approximately 12 weeks, or withdraws her/his consent. The patient may be followed up after the trial if an AE/SAE related to the study is not resolved when the intervention ends. In that case, the patient will be offered to be followed up by telephone until a solution is found or until it terminates.

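### No named endpoint compares FMT with placebo for grade 2+ or serious adverse events after day 7, and the week 5–8 window does not fit Table 1

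*Protocol*

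**What the plan says.** Safety is the primary hypothesis (section 2.3.1). The adverse-event endpoints are:

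- Primary (2.4.1): "Number of adverse events of severity grade 2 or more assessed by CTCAE v5.0 during the first week after first intervention".
- Endpoint 8 (2.4.2): "Mild adverse events (grade 1) following FMT or placebo assessed by CTCAE v5.0". No window is given.
- Endpoint 9 (2.4.2): "Adverse events in week 5-8".
- Endpoint 10 (2.4.2): "Serious adverse events during longterm follow-up".

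Endpoints 8 to 10 stand under one source line: "Patient-reported measures from the schedule of side effects and telephone call 1 week after each intervention". Section 3.6.4 has the side-effect report kept for 7 days. Separately, section 6.1.1.1 states: "All AE, AR, SAE and SUSAR are documented in patient-specific case report form (CRF) at the clinical attendances", or at the one-week call.

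Placebo control exists only in the "first 4 weeks where patients receive either FMT or placebo" (3.1). After that, everyone receives FMT.

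Two calendars appear. Section 3.1 describes an eight-week trial of two 4-week periods, hypothesis 4 in 2.3.2 separates the doses by 4 weeks, and Figure 1 places the second dose at the end of week 4. Table 1 puts the first dose in week 1, the repeat investigations in week 5 (+1), the second dose in week 6 (+2) and visit 8 in week 10 (+2). Section 6.1.1.1 ends a participant's connection to the study once they have "completed the second intervention period, after approximately 12 weeks".

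**The concern.** The trial exists to supply safety data for a larger study, and its randomised safety evidence can come only from the time before the second dose. The grade 2+ endpoint stops after one week of that time. The next window that admits grade 2+ events is tied to calendar weeks and not to a dose, and endpoint 10 starts after both arms have had FMT.

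Section 6.0 lists harms that need not be confined to the first week: symptoms compatible with bacterial overgrowth in about 1 in 20 patients, and severe long-term symptoms of donor-derived infection in under 1%. The protocol gives no onset times, so later onset is an assumption, but sections 2.5 and 2.6.4 raise slow transit and reduced resistance to infection as reasons for caution.

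If endpoint 9 is applied literally to the Table 1 calendar, it also takes in the repeat motility capsule, CT and breath test of visits 5 and 6. Section 6.1.1.3 lists abdominal pain, nausea and diarrhoea as capsule side effects. Nausea and diarrhoea are also on the FMT list in section 6.0.

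**Working it through.** The plan gives no figure to reproduce here; section 4.1 says that the assumptions for a formal power calculation are absent. The check is a day count.

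**Convention (assumed).** The first dose is on day 1, week *w* starts on day 7(*w* − 1) + 1, and the second dose falls at the start of its week. Weeks 5–8 are then days 29 to 56. Another convention moves the counts by up to about a week; the mismatch remains.

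**Eight-week calendar (3.1, 2.3.2, Figure 1).** The second dose is on day 29.

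- Controlled period: 28 days. The primary window covers 7/28 = 25%.
- Days 8 to 28, which is 28 − 7 = 21 days (75%), lie in no endpoint that admits grade 2+ or serious events.
- Weeks 5–8 coincide with the 28 days after the second dose (100%).

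**Table 1 calendar.** The second dose is in week 6, 7 or 8. The controlled period is the second-dose day minus 1. Pre-dose days in the window are the second-dose day minus 29; post-dose days are 57 minus the second-dose day.

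| Second dose | Day | Controlled days | Covered by primary | Weeks 5–8: days before dose 2 | Weeks 5–8: days after dose 2 | Share of the 28 days after dose 2 |
|---|---|---|---|---|---|---|
| Week 6 | 36 | 35 | 7/35 = 20% | 7 | 21 | 75% |
| Week 7 | 43 | 42 | 7/42 = 17% | 14 | 14 | 50% |
| Week 8 | 50 | 49 | 7/49 = 14% | 21 | 7 | 25% |

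On this calendar endpoint 9 does reach the last 7 to 21 controlled days, but it pools them with open FMT time, so it yields no clean FMT-versus-placebo contrast. Days 8 to 28 stay uncovered on either calendar.

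**Does endpoint 8 close the gap?** No. It is limited to grade 1, and its stated source is the one-week schedule and call.

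**Is the 12-week figure decisive?** No; its starting point is not stated. From the first dose it fits the outer edge of visit 8 in Table 1 (10 + 2 = 12). From the inclusion visit three weeks earlier, an eight-week trial gives 3 + 8 = 11, also close. The conflict rests on Table 1.

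**The case against.** The strongest reply is that delayed harm is not ignored, and much of this stands.

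- **Other endpoints see some of it.** The breath test (endpoint 19) is done 4 weeks after the first intervention and before the second dose, so it is a placebo-controlled measure related to bacterial overgrowth. GSRS-IBS and PAGI-SYM at week 4 would show worsening symptoms. Endpoint 10 covers late serious events. A reader might infer that delayed harm has no valid endpoint at all; the documents do not support that.
- **A serious event on day 15 is not lost.** It goes into the CRF (6.1.1.1), serious events are fully monitored (6.1), unexpected serious reactions are reported within 24 hours (6.1.1.1, 6.1.1.2), and there are annual safety reports. Section 4.2 promises a descriptive safety profile with no one-week limit. What is missing is a named comparison.
- **The label may simply mean the second period.** Section 2.4.2 itself counts week 4 and week 8, and Figure 1 labels the second period in the same way. So it cannot be said that test-related events will be counted as second-dose events; that follows only from a literal reading on Table 1.
- **The two sizes belong to different calendars.** The 75% gap uses the eight-week calendar, on which weeks 5–8 fit. The 1-to-3-week overlap uses Table 1, on which the controlled period exceeds 28 days. They must not be added.
- **Visit 8 is anchored.** Applying the Table 1 windows independently suggests that visit 8 could fall 2 to 6 weeks after the second dose, but section 3.6.7 places it 4 weeks after, and the nominal weeks 6 and 10 agree.
- **One week suits the primary endpoint.** Section 6.0 says that reactions such as fever and discomfort mostly last under a day.

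None of this supplies a grade 2+ or serious-event comparison between arms after day 7, or makes the second window correct on both calendars.

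**Conclusion.** The point holds in limited form. No named endpoint compares the arms for grade 2+ or serious adverse events after the first week of the only controlled period: 21 of 28 days on the eight-week calendar, and at least days 8 to 28 on Table 1. Endpoint 9 is sound on one of the protocol's calendars and misplaced by 1 to 3 weeks on the other.

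The endpoints and their windows are set in the protocol, so this is not a detail left to the SAP, although the SAP, which is not shown, may well tabulate all events.

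The severity is should-fix. Participants remain monitored, the data are due to be recorded, and the comparison would be descriptive in any case. With 10 FMT patients in the controlled period (the split suggested by Figure 1), the chance of seeing at least one event of 1-in-20 frequency is 1 − 0.95^10 = 40%. That limits what a longer window can show, but is no reason to leave most of the controlled time without an endpoint. The day counts rest on the week convention stated above.

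**What to change.** 1. Keep the week-1 primary endpoint.
2. Add a secondary endpoint: *patients with any grade 2+ adverse event, and patients with any serious adverse event, from the first dose until immediately before the actual second dose, FMT versus placebo*. It should end at the second dose and not at visit 5; on Table 1, ending at visit 5 would leave the time up to the second dose, including visit 6, in neither window.
3. Redefine endpoint 9 as *adverse events from the actual second dose to visit 8*.
4. Name the CRF entries made at attendances and calls (6.1.1.1) as the source for both, since the one-week schedule and call cannot cover them alone.
5. Reconcile the week numbering in 2.3.2, 2.4.2, 3.1, Table 1, 6.1.1.1 and Figure 1. Which dosing calendar applies is for the sponsor to settle; windows anchored to actual doses work on either.

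The cost is protocol wording and one more descriptive comparison, with no new visits. Two limits should be stated: events after day 7 are collected by recall and not by daily report, and the window will vary in length between patients, so days at risk should be shown by arm. The change should be made before unblinding.

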## 2.6 Background

### 2.6.1 Severe gastrointestinal neuropathy in diabetes mellitus

DM1 is strongly associated with diarrhea, nausea, vomiting, abdominal pain, bloating, constipation and faecal incontinence(1, 2). Though the severity of symptoms varies, severe cases suffer from daily uncontrollable diarrhea, vomiting, intense nausea, and faecal incontinence with severe consequences for social activities and quality of life(3). Additionally, nightly uncontrolled bowel movements pose a clinical challenge.

Earlier studies of patients with DM1 have demonstrated demyelination, axonal damage and reduced number of motor fibers in vagal nerves(4-6). Other studies report degeneration of nerve fibers within the enteric nervous system, including the Cajal cells (the pacemaker cell of the bowel)(7, 8). Today, it is assumed that diabetic gastrointestinal (GI) dysfunction is caused by autonomic neuropathy, dysfunction of the Cajal cells, and reduced contractility of the intestinal smooth muscle cells(7-9). The clinical effect of each component remains unknown.

### 2.6.2 Intestinal microbiota in diabetes mellitus type 1

Several studies have compared the gut microbiota of patients with early DM1 or even at a prediabetic stage with those of healthy volunteers. Findings have not been conclusive, but most have found reduced diversity of the intestinal bacterial community and increased proportion of *Bacteroides*(10). Preclinical studies support the hypothesis that specific features of the microbiota give rise to impaired intestinal permeability(11), which further influence T cell autoimmunity and B-lymphocytes.

This may lead to beta-cell destruction and DM1. However, most research on gut microbiota and DM has been in DM type 2. Thus, the impact of the microbiota in humans with DM1 and GI symptoms remains obscure

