### 3.3 Analyses

#### 3.3.1 Assessment of gastrointestinal symptoms

a) Patients will fill in a daily bowel diary, commonly used at our unit and a side effect schedule which will be handed out to the patients in paper form. The patients will fill out the diary and side effect schedule for one-week diary four times: at baseline, during the first week of each intervention period, and at longterm follow-up after 26 weeks. The diary contains questions that include number of daily bowel movements, consistency of stools (Bristol stool chart), time spent at defecation, nightly bowel movements, episodes of faecal incontinence, days with abdominal bloating/pain and the amount of insulin used. The side effect schedule will contain a schedule of commonly known side effects and an assessment of the severity of the side effect (appendix 2).

The following four questionnaires will be filled out by the patient on an Ipad during the scheduled visits and the data will be saved directly in REDCcap.

- b) GSRS-IBS: The Gastrointestinal syndrome rating scale irritable bowel syndrome version (GSRS-IBS) is a 13-item questionnaire developed and validated for irritable bowel syndrome(25). The items cover some of the most common bowel symptoms experienced by patients with DM1. These include pain, bloating, diarrhea, constipation and gas. The questionnaire adds to a total score which covers the previous week. The questionnaire has been developed and validated in a Nordic country (Sweden), translated into Danish and subsequently used in several studies from our unit at AUH (appendix 3).
- c) PAGI-SYM: The patient assessment of upper gastrointestinal symptom severity index (PAGI-SYM) questionnaire has been developed and validated for functional dyspepsia(26). The questionnaire is composed of 20 items with 6 subscales: heartburn/regurgitation, nausea/voliting, fullness/satiety, bloating, upper abdominal pain and lower abdominal pain. PAGI-SYM scores have been shown to correlate with gastric emptying rate and gastric hypersensitivity and therefore may be useful in the evaluation of gastroprokinetics(26) (appendix 4).
- d) IBS-IS: The irritable bowel syndrome impact scale (IBS-IS) is a 26-item questionnaire developed to capture the impact of irritable bowel syndrome and its treatment on patients' lives(27). The 26-items represent five domains: Fatigue. Impact on daily activities, sleep disturbance, emotional distress and eating habits (appendix 5).

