# 5.1 Inclusion criteria

- Adult ( $\geq$  18 years old), male or female patients with DM1 for at least 5 years and
- Average of or above 40 points in the questionnaire: Gastrointestinal syndrome rating scale irritable bowel syndrome version (GSRS-IBS).

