## 6.1.1 Adverse events

Adverse events are defined according to the ICH Harmonized Tripartite Guide to Good Clinical Practice (https://www.ema.europa.eu/en/documents/scientific-guideline/ich-e-6-r2-guideline-good-clinical-practice-step-5\_en.pdf).

- Adverse Event (AE): any untoward medical occurrence in a patient which does not necessarily have a causal relationship with the trial
- Adverse reaction (AR): any adverse and undesirable reaction to the experimental treatment, regardless of dose.
- Unexpected adverse reaction (UAR): a side effect whose nature or severity does not match the expected side effects of the trial.
- Serious Adverse Event (SAE) or serious adverse reaction (SAR): any adverse event or adverse reaction that results in:
  - 1. death or
  - 2. a serious deterioration in health that
    - resulted in life-threatening illness or injury
    - resulted in permanent impairment of body structure or body function
    - required hospitalisation or prolongation of existing hospitalisation
    - resulted in medical or surgical treatment to prevent the above

- foetal death, congenital anomaly or birth defect or any other negative effect on the foetus.

- Suspected Unexpected Serious Adverse Reaction (SUSAR): a suspected but unexpected serious adverse reaction that has not been previously described for the treatment with FMT according to published science.

All patients with expected or unexpected events or side effects are offered admission to the treatment ward if necessary. Furthermore, all unexpected side effects and AE will be reported in the "Adverse Event CRF" containing following information:

1. Degree of difficulty (mild, medium, severe)

- 2. Relation to the investigation (expected/unexpected)
- 3. Duration (start date, end date, are the condition persistent after the last examination)
- 4. The graduation of the adverse event according to the CTCAE v0.5

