#### 6.1.1.3 Wireless Motility Capsule

The WMC is an orally ingested data recording device that enables simultaneous assessment of regional and whole gut transit. The WMC is CE marked and approved by the US Food and Drug Administration for evaluation of patients with suspected delayed gastric emptying and evaluation of colonic transit time in patients with chronic constipation. The WMC is contraindicated to patients with a history of gastric bezoar, swallowing disorders, dysphagia to food or pills, suspected

stricture or fistulae along the GI tract, physiological GI obstruction, GI surgery within the previous 3 months, Crohn's disease, diverticulitis or an implanted or portal electromechanical medical device(31).

The most serious AEs associated with the WMC are the inability to confirm passage of the capsule outside the body, capsule retention and obstruction. In a previous trial with nearly 6000 patients receiving WMC there were 20 reports of prolonged capsule retention (5 in the stomach, 2 in the small intestine and 13 in the colon) which yield a retention rate of 0,33%(30). An upper endoscopy was required for extraction of the 5 capsules that were retained in the stomach. Of the remaining 15 cases, only 1 capsule required drug intervention. The other 14 capsules passed spontaneously. None of the patients required surgical intervention. If it cannot be confirmed that the capsule has passed five days after ingestion the manufacturer's follow-up recommendations should be followed. This is based on the location of the capsule which is determined by the pH profile obtained during the study. If the pH profile suggests that the capsule is retained in the stomach or bowel. Due to the low risk of obstruction once the capsule is in the colon, no specific follow-up is necessary if the capsule is retained in this area.

Other side effects associated with WMC include abdominal pain, dysphagia, nausea and diarrhea. However, as many of the patients had these symptoms at baseline, these side effects have been difficult to determine if they were caused by the WMC. Patients are provided information about the risks in the participants information sheet, which they are urged to read comprehensively prior to consenting to participate.

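### The primary endpoint counts every grade 2 or higher event in week 1 with no baseline reference, in patients whose entry symptoms overlap the expected FMT side effects

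*Protocol*

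**What the plan says.** The primary endpoint (Protocol 2.4.1) is "Number of adverse events of severity grade 2 or more assessed by CTCAE v5.0 during the first week after first intervention". An adverse event (6.1.1) is "any untoward medical occurrence in a patient which does not necessarily have a causal relationship with the trial", and nothing is said there about pre-existing or worsened conditions. The nearest item to causality on the adverse event form is "Relation to the investigation (expected/unexpected", which cannot separate disease symptoms from capsule effects.

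Entry (5.1) requires "Average of or above 40 points in the questionnaire" GSRS-IBS, which section 3.3.1 describes as covering pain, bloating, diarrhoea, constipation and gas. The background (2.6.1) says that "severe cases suffer from daily uncontrollable diarrhea, vomiting, intense nausea, and faecal incontinence". Section 6.0 expects transient diarrhoea, nausea or bloating in about one-third of patients given FMT.

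On baseline data, section 3.3.1 says: "The patients will fill out the diary and side effect schedule for one-week diary four times: at baseline". The visit text differs. Sections 3.6.1 and 3.6.2 mention only the bowel diary, Table 1 has no row for the side effect schedule, and the side effect report first appears at visit 4 (3.6.4).

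**The concern.** On the recording form, a patient's usual diarrhoea or bloating and a reaction to the capsules can look the same. With no reference week in the definition, both count towards the primary endpoint if graded 2 or more.

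The protocol recognises this difficulty for the motility capsule: "as many of the patients had these symptoms at baseline, these side effects have been difficult to determine" (6.1.1.3). It also compares the diary and questionnaire endpoints with baseline (2.4.2, endpoints 1 to 7 and 11 to 13), but not the primary endpoint.

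The primary hypothesis (2.3.1) is that FMT is safe and well tolerated, and section 4.2 plans a descriptive summary of adverse events by median and interquartile range. The absolute count in the FMT arm is therefore likely to be read as the safety figure, and it is the quantity that background symptoms inflate directly.

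**Working it through.** The protocol states no alpha, power, event rate or margin, and section 4.1 says that the assumptions for a power calculation are lacking. There is no figure of its own to reproduce. What follows is illustration.

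**Inputs.** From the protocol: 20 patients, 10 per arm as read from Figure 1, and about one-third of FMT patients with transient symptoms (6.0, CTCAE grade not stated). Assumed: background rates, added events, two-sided 5% tests.

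**1. Counts.** Let b be the background grade 2+ events per patient-week, the same in both arms. Added events are 1.0 (FMT) and 0.1 (placebo), and counts are Poisson.

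- Mean count, FMT arm: b + 1.0
- Mean difference: (b + 1.0) − (b + 0.1) = 0.9 for every b
- Ratio: (b + 1.0)/(b + 0.1)
- SD of the difference in means: √[((b + 1.0) + (b + 0.1))/10] = √[(2b + 1.1)/10]
- Power: simulated Mann-Whitney test, good to a point or two

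| b | FMT mean | Difference | Ratio | SD of difference | Power |
|---|---|---|---|---|---|
| 0 | 1.00 | 0.9 | 10 | 0.33 | 75% |
| 0.25 | 1.25 | 0.9 | 3.6 | 0.40 | 57% |
| 0.5 | 1.50 | 0.9 | 2.5 | 0.46 | 43% |
| 1 | 2.00 | 0.9 | 1.8 | 0.56 | 31% |
| 2 | 3.00 | 0.9 | 1.4 | 0.71 | 19% |
| 4 | 5.00 | 0.9 | 1.2 | 0.95 | 12% |

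The difference in means does not move. The absolute count, the ratio and the precision do.

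**2. Patients with at least one event.** Let p be the background proportion and q = 1/3 the proportion with an FMT-caused event, taking the section 6.0 figure as all grade 2 or more (an assumption). Then P(FMT) = 1 − (1 − p)(1 − q), and the difference from placebo is q(1 − p). Power is exact Fisher, 10 against 10.

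| p | FMT | Placebo | Difference (points) | Power |
|---|---|---|---|---|
| 0 | 33% | 0% | 33 | 21% |
| 0.1 | 40% | 10% | 30 | 15% |
| 0.3 | 53% | 30% | 23 | 7% |
| 0.5 | 67% | 50% | 17 | 4% |
| 0.9 | 93% | 90% | 3 | 0.1% |

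On this scale the visible difference itself shrinks. Power is only 21% even with no background.

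**3. Would subtracting the baseline count help?** This was simulated with 20,000 runs and t-type tests. Each patient had an own gamma-distributed background rate, the same in both weeks, and FMT added one event.

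| Mean background | Gamma shape | Raw count | Count minus baseline | Baseline as covariate |
|---|---|---|---|---|
| 0.5 | 1 | 50% | 42% | 51% |
| 0.5 | 4 | 55% | 42% | 53% |
| 2 | 1 | 15% | 18% | 21% |
| 2 | 4 | 21% | 17% | 22% |
| 4 | 1 | 7% | 12% | 13% |
| 4 | 4 | 11% | 12% | 13% |

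Subtraction loses power at low background and gains little at high background. In the same model, a rule that removed all background would give about 93%. That is an upper bound, because symptoms that fluctuate between weeks would still produce some new or worsened events.

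**The case against.** Four objections deserve weight.

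- **The trial is randomised, double-blind and placebo-controlled in the first period.** This stands for the difference in mean counts, which stays unbiased. It does not rescue the ratio, the difference in proportions, the precision or the absolute count.
- **The SAP, not shown, may restrict the analysis to treatment-emergent events.** It may, and section 4.2 leaves analysis details to it. Appendix 2, the side effect schedule, is not shown either and may tell patients how to treat usual symptoms. But section 2.4.1 as worded counts everything. Whether usual diarrhoea is recorded as an event, and whether a baseline schedule exists, is settled at data capture and cannot be fully repaired later.
- **Power is a poor yardstick for a descriptive pilot.** Largely true. No test of adverse events is planned, the 1.0 against 0.1 contrast is assumed, and the small sample limits detection as much as background does. The argument about the absolute count needs no power calculation.
- **The overlap is not complete.** Nausea is not among the GSRS-IBS symptoms listed in section 3.3.1, and no single symptom is required for entry. Diarrhoea and bloating do overlap, and section 2.6.1 lists nausea and vomiting among severe cases.

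A reader might infer that pre-existing symptoms will swamp any FMT signal. The documents do not support that. They give no weekly rate of grade 2+ events, and over the assumed range the loss runs from moderate to near total. A reader might also infer that the comparison is biased against FMT or that serious harm would be hidden. Neither follows: background enters both arms alike, and serious events and event types absent at baseline remain visible.

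**Conclusion.** The point holds as a weakness in the endpoint definition that should be corrected. Followed as written, section 2.4.1 mixes pre-existing symptoms with events after the intervention, in a population selected for overlapping symptoms. The count in the FMT arm then cannot be read as a safety figure on its own, and the contrast with placebo is noisier than it need be.

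The direction is firm, but the size is not. In the illustration, power falls to somewhere between 57% and 12% as the background runs from 0.25 to 4 events per patient-week. This rests on Poisson counts, equal background in both arms, 10 patients per arm and the assumed added events.

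**What to change.** In section 2.4.1, define the primary endpoint as CTCAE grade 2 or higher events in the week after the first intervention that are new, or worse by at least one grade, compared with the baseline-week side effect schedule. Apply the rule event by event and do not subtract counts. Report the all-events count by arm as supportive, so that an event matching a baseline symptom in type and grade is still shown.

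Reconcile section 3.3.1 with Table 1 and sections 3.6.1, 3.6.2 and 3.6.4, so that the side effect schedule is handed out and completed at baseline. State which week is the reference. Section 3.6.2 starts the baseline diary at visit 2, when the motility capsule is swallowed, and section 6.1.1.3 lists abdominal pain, nausea and diarrhoea among that capsule's side effects.

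This is a cheap improvement: one sentence in 2.4.1, a row in Table 1 and matching visit text. The downside is small, one week of a paper form at baseline, which section 3.3.1 already intends.
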